3.1.7.2 Missing start and end dates for AE and concomitant medication (CM)

The assumption will be the worst or most conservative judgment when imputing AE and CM start and end dates. The purpose of imputing a start date is to help define whether the AE/CM started while taking study drug.

For a partial or missing start date:

- If the day is missing, the first day of the month will be imputed. If the missing day is the same as the month of first dose of study drug, then the first dose date will be imputed.
- If the day and month are missing, the first day of January will be imputed. If the year is the same as the first dose date, then the first dose date will be imputed.
- If the day is completely missing, the first dose date will be imputed. If the end date suggests it could have started prior to this, the first day of January of the same year as the end date will be imputed.
- When imputing a start date, the start date will ensure that the new imputed date is sensible, i.e., is prior to the end date of the AE or CM.

For a partial or missing end date:

- If the day is missing, the last day of the month or the last assessment date, whichever is earlier, will be imputed.
- If the day and month are missing, the 31st of December or the last assessment date, whichever is earlier, will be imputed.
- If the date is completely missing, there will be a need to look at whether the AE/CM is still ongoing before imputing a date. If the ongoing flag is missing, then it will be assumed that AE is still present, or CM is still being taken (i.e., do not impute a date). If the AE/CM has stopped, then the last assessment date will be imputed.

These data imputations are for categorization purpose only and will not be used in listings.

If the assessment of the relationship of the AE to belumosudil is missing, then it will be assumed that the AE is related to belumosudil and the AE considered as such in the frequency tables of possibly related AEs. No imputation should be done at the data level.

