2.4 Treatment Descriptions

The treatment groups will be described below and used for different analysis.

KQD: KD025 200mg QD for the first 28 weeks

KBID: KD025 200mg BID for the first 28 weeks

PBO: Placebo for the first 28 weeks

KQD/KQD: KD025 200mg QD for the first 28 weeks and KD025 200mg QD from week 28 to 52.

KBID/KBID: KD025 200mg BID for the first 28 weeks and KD025 200mg BID from week 28 to 52.

K: KD025 200mg for the first 28 weeks

PBO/KQD: Placebo for the first 28 weeks and KD025 200mg QD from week 28 to 52.

PBO/KBID: Placebo for the first 28 weeks and KD025 200mg BID from week 28 to 52.

KQD_C: KD025 200mg QD for the first 28 weeks combined with subjects that switched from placebo to KD025 200mg QD from week 28 to 52.

KBID_C: KD025 200mg BID for the first 28 weeks combined with subjects that switched from placebo to KD025 200mg BID from week 28 to 52.

K_C: KD025 200mg for the first 28 weeks combined with subjects that switched from placebo to KD025 200mg from week 28 to 52.

All KD025 200mg QD: KD025 200mg QD for the first 52 weeks combined with subjects that switched from placebo to KD025 200mg QD from week 28 to 52.

All KD025 200mg BID: KD025 200mg BID for the first 52 weeks combined with subjects that switched from placebo to KD025 200mg BID from week 28 to 52.

All KD025: KD025 200mg for the first 52 weeks combined with subjects that switched from placebo to KD025 200mg from week 28 to 52.

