3.2 Analysis Populations

Three populations will be employed in the analysis of study data:

- The Modified Intent-to-treat (mITT) Population will consist of all subjects who receive at least 1 dose of study drug.
- The Evaluable for Efficacy/Activity Population will consist of subjects who have received at least 80% of expected study drug and have post-baseline efficacy data.
- The Safety Population is defined as all subjects who receive at least 1 dose of study drug. In this study, the Safety Population is equivalent to the mITT Population.

The primary endpoint will be analyzed on the modified Intent-to-Treat (mITT) Population.

Demographics, subject disposition, baseline characteristics, and efficacy analyses will be summarized in mITT Population and by group.

All safety analyses will be performed on the safety population.

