3.9.1 Adverse Events

AEs will be coded using the MedDRA dictionary (Version 22.0 or higher). TEAEs are any AEs occurring or worsening in severity after the first administration of study medication. All AEs (including SAEs) will be graded using the 5-point CTCAE V5.0 scale (mild, moderate, severe, life threatening, or death). Causality with study treatment will be classified as: definitely related; probably related; possibly related; unlikely related; not related.

The number (N) and percentage (%) of patients who experienced at least one TEAE will be summarized by dose group, including tabulation by:

- SOC and PTs within each SOC in decreasing total frequency
- PT in decreasing total frequency
- SOC, PTs, and maximum severity
- SOC, PTs, and relationship to study drug

These analyses will be repeated for Grade ≥3 TEAEs, SAE, TEAEs leading to dose modification, and AE leading to study drug discontinuation.

Subject listings will be provided for AEs, SAEs, AEs resulting in study drug discontinuation and deaths. Time to onset and duration of AEs will be included in listings, along with action taken and outcome.

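### The AE start-date rules have no anchor at the first belumosudil dose, so some poorly dated open-label events in placebo switchers are dated to the placebo period

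*SAP*

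**What the plan says.** SAP 3.1.7.2 states its principle first: "The assumption will be the worst or most conservative judgment when imputing AE and CM start and end dates". Its start-date rules are then as follows.

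- Day missing: "If the day is missing, the first day of the month will be imputed". The exception is "If the missing day is the same as the month of first dose of study drug, then the first dose date will be imputed".
- Day and month missing: 1 January of the reported year. The exception is "If the year is the same as the first dose date, then the first dose date will be imputed".
- No date: "If the day is completely missing, the first dose date will be imputed", unless the end date points to an earlier start.

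SAP 3.9.1 uses the same anchor for treatment emergence: "TEAEs are any AEs occurring or worsening in severity after the first administration of study medication". Placebo counts as study drug, because "The Safety Population is defined as all subjects who receive at least 1 dose of study drug" and SAP 3.2 equates this population with the mITT.

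Placebo subjects (20 planned) are re-randomised to belumosudil at the end of Week 28, Day 197 (Protocol 4.3 and 5.2.9). SAP 2.4 then defines belumosudil groups that include them: KQD_C, KBID_C, K_C and three All KD025 groups, for example "All KD025: KD025 200mg for the first 52 weeks combined with subjects that switched from placebo to KD025 200mg from week 28 to 52".

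**The concern.** A table of AEs on belumosudil that includes switchers needs to know when belumosudil began for each of them. SAP 3.1.7.2 and 3.9.1 know only when study drug began, about 28 weeks earlier. A poorly dated event that truly arose on belumosudil can therefore receive a start date at which the subject was on placebo, and so drop out of the belumosudil column.

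Elsewhere the SAP does allow for the switch. Section 3.1.6 resets baseline at the first belumosudil dose for these subjects, and 3.1.7.1 keeps LOCF within treatment period for them. Section 3.1.7.2 itself counts an AE with missing causality as related to belumosudil. Dating undated events to the first placebo dose goes the other way, which suggests an oversight. At stake is the completeness of the pooled safety summary in what Protocol 9.1 calls the first study in this population.

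**Working it through.** The plan gives no figure to reproduce, so the check applies the rules literally to a placebo subject who switches on schedule.

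**Inputs from the documents**
- Switch: Day 28 × 7 + 1 = 197 (Protocol 5.2.9).
- End of treatment: Day 365. AE reporting runs 28 days further, to Day 393 (Protocol 9.1).
- Open-label days at risk: 365 − 197 + 1 = 169; to Day 393, 393 − 197 + 1 = 197.

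**Assumptions, not in the documents**
- True onset is uniform over the open-label days.
- First doses are spread evenly over the calendar (every day of a four-year cycle).
- An event goes to placebo if its imputed start precedes the first belumosudil dose.
- No end date overrides the imputation.

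**Only the day missing.** The event moves to the 1st of its own month. That precedes the switch only if the event is in the switch month. With a switch on day s of a month of L days, L − s + 1 days are affected (none if s = 1). The average is (29 + 28 + … + 1)/30 = 14.5 days for a 30-day month and 15 for a 31-day month; over the calendar it is about 14.7.
- To Day 365: 14.7/169 = 8.7%.
- To Day 393: 14.7/197 = 7.5%.
- So about 91% of these events stay in the correct period.

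**Day and month missing.** Every event in the calendar year of the switch is misdated. It goes to the first placebo dose if the first dose was in that year, and otherwise to 1 January, which also precedes the switch. Events in the following year go to 1 January of that year and are placed correctly. The share is the number of days from the switch to 31 December (at most 169) divided by 169.
- First dose 15 January 2021, switch 30 July: 155/169 = 92%.
- First dose 15 June 2021, switch 28 December: 4/169 = 2%.
- First dose 15 July 2021, switch 27 January 2022: all 169 days fall in 2022, so 100%. The same holds for mid-month first doses through December.
- Calendar average: 77% to Day 365, 73% to Day 393.

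**No start date.** The event goes to the first placebo dose: 169/169 = 100%.

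**Which rule does this.** The exception for the month of first dose, read as month and year, applies to 0% of open-label events, because that month lies about 28 weeks before the switch. The misdating comes from the first-of-month rule with no switch-month exception, the year-only rule and the no-date rule.

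**With a second anchor at the first belumosudil dose,** the share misdated is 0% in all three classes.

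**Spill-over into Week 24.** Only about 0.1% of day-missing open-label events would be dated on or before Day 169. The Week 24 comparison is exposed almost only through year-only and undated events.

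**The case against.** The strongest reply is that this will hardly ever matter. At most 20 subjects are affected, visits are at least every four weeks, Protocol 9.3.4 requires an onset date for every AE, and imputed dates serve categorisation only. An AE that worsens after the switch is entered as a new AE with its own onset date, so it is kept if that date is complete. Even a misdated event remains a TEAE under SAP 3.9.1. All of this stands, and it keeps the point small. The rules still give a wrong period when they are used.

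Three stronger readings are tempting, and the documents do not support them.

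- *A reader might infer that all partly dated open-label events go to placebo.* Most day-missing events do not. Moreover, the SAP never states how an AE is assigned to a period, so assignment by imputed start date is an inference. That silence is itself a gap.
- *A reader might infer that pooled tables both lose belumosudil events and absorb placebo-period ones.* These need opposite readings. If every TEAE since the first dose of any study drug is counted, a misdated event is still counted. If switchers contribute only their belumosudil period, placebo-period events stay out. SAP 2.4 describes switchers as contributing Weeks 28 to 52, which favours the second reading, and so under-counting.
- *A reader might infer that pooling inflates belumosudil percentages against placebo.* Suppose a 20% risk per 28 weeks, constant hazard, full follow-up and no drug effect. All KD025 would show (40 × 33.9% + 20 × 17.4%)/60 = 28.4%, using 1 − 0.8^(52/28) = 33.9% and 1 − 0.8^(24/28) = 17.4%. But K_C would show (40 × 20% + 20 × 17.4%)/60 = 19.1%, with no excess, and the SAP nowhere sets All KD025 against 28 weeks of placebo. Its stated TEAE comparison is at Week 24 (SAP 3.8.2.7). The gap is not a measure of bias in this plan.

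**Conclusion.** The point holds in a narrow form. SAP 3.1.7.2 and 3.9.1 have no anchor at the first belumosudil dose for placebo switchers. Their belumosudil-period AEs are dated to placebo when only the day is missing in the switch month, when only the switch year is known, or when there is no start date. Among belumosudil-period events every such error runs from belumosudil to placebo, contrary to the section's stated principle.

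The shares of 8.7%, 77% and 100% rest on uniform onset, evenly spread first doses and assignment by imputed date. They are shares of events with that kind of incomplete date, not of all AEs. The absolute number cannot be derived from the documents. Subjects randomised to belumosudil are unaffected. This is a minor correction, worth making before database lock because it is cheap and removes room for two programmers to produce different tables.

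**What to change.** Add two rules, limited to the belumosudil-exposure tables that include switchers (KQD_C, KBID_C, K_C and the All KD025 groups).

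1. In a switcher, a TEAE is an AE with onset or worsening on or after the first belumosudil dose.
2. In a switcher, impute the first belumosudil dose date when the partial start date is compatible with the month or year of that dose, or when the start date is missing, unless the AE ended before the switch.

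Keep the existing first-dose rules for the double-blind Week 24 and Week 28 comparisons. Applied there, the second rule would remove true placebo events from the randomised placebo arm.

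Optionally, add events per patient-year to the All KD025 tables only, since they mix up to 52 with up to 24 weeks of exposure.

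The cost is a few SAP sentences, some programming and perhaps one column. Some true placebo-period events with incomplete dates will count as belumosudil events in the pooled tables, which is the conservative direction. The same undated event may also appear under placebo in a double-blind table and under belumosudil in a pooled one, so a footnote should say so. Trial conduct does not change.

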3.2 Analysis Populations

Three populations will be employed in the analysis of study data:

- The Modified Intent-to-treat (mITT) Population will consist of all subjects who receive at least 1 dose of study drug.
- The Evaluable for Efficacy/Activity Population will consist of subjects who have received at least 80% of expected study drug and have post-baseline efficacy data.
- The Safety Population is defined as all subjects who receive at least 1 dose of study drug. In this study, the Safety Population is equivalent to the mITT Population.

The primary endpoint will be analyzed on the modified Intent-to-Treat (mITT) Population.

Demographics, subject disposition, baseline characteristics, and efficacy analyses will be summarized in mITT Population and by group.

All safety analyses will be performed on the safety population.

3.3 Subject Disposition and Evaluability

A disposition of all enrolled subjects will be summarized. The number of subjects screening failed, discontinuing from study treatment, discontinuing from study and the primary reason for discontinuation will be summarized.

3.4 Protocol Deviations

All protocol deviations will be identified and classified as major or minor before the clinical database lock and will be presented in a listing.

Major Deviation: Protocol deviation that may impact the accuracy, and/or reliability of the study data or that may impact subject rights, safety or well-being.

Minor Deviation: Protocol deviation that does not impact the accuracy, and/or reliability of the study data or subject rights, safety or well-being.

3.5 Demographics and Baseline Characteristics

3.5.1 Demographics and Other Characteristics

A summary table and a by patient listing will be generated for patient demographics and other characteristics. Variables to be included are: age, sex, race, ethnicity, height, weight, body mass index (BMI), if subjects with ILD (display ILD confirmed diagnosis date in listing), child bearing potential, and other variables as applicable based on indication/study design.

Demographics and other baseline characteristics will be summarized by treatment group in each population.

3.5.2 Medical History

Medical history (except ILD) will be summarized by primary system organ class (SOC) and preferred term (PT). Medical history will be coded using Medical Dictionary for Regulatory Activities (MedDRA, Version 22.0 or higher) terminology.

Medical history will be presented in a listing by patient and summarized by treatment group in the Safety Population.

3.6 Concomitant Medications

Concomitant medications will be coded using World Health Organization (WHO) Drug Dictionary. Concomitant medications are all medications taken after the start of study consent, during the treatment period (day 1 until 28 days after last dose), including those started before but ongoing at the start of study treatment.

Concomitant medications will be summarized according to Anatomical Therapeutic Class (ATC) and preferred drug name.

Concomitant medications will be presented in a listing by patient and summarized by treatment group in the Safety Population.

3.7 Treatment Compliance and Exposure

The relative dose intensity (RDI) will be used to assess the treatment compliance. The RDI is defined as:

RDI (%) = $100 \times ADI (mg/day) / PDI (mg/day)$,

where ADI and PDI are the actual dose intensity and planned dose intensity, respectively:

PDI (mg/day) = planned cumulative dose (mg) / duration of exposure (days),

ADI (mg/day) = actual cumulative dose (mg) / duration of exposure (days).

The planned cumulative dose is the planned daily dose amount multiplied by the duration of exposure, while the actual cumulative dose is the sum of actual total daily dose amount over the duration of exposure. The actual total daily dose will need the information of dose modifications (increased and reduced) and dose interruption (held) captured in CRF (Dose Modifications and Interruptions). If a subject does not take any study drug, the actual RDI by definition is zero.

The duration of exposure is defined as:

Duration of exposure (days) = (Date of last dose – Date of first dose) + 1, regardless of unplanned intermittent discontinuations.

One summary table will be generated for treatment exposure and compliance, including: treatment duration (weeks), treatment duration categories (0 to 12 weeks, 12 to 24 weeks, 24 to 28 weeks, 28 to 40 weeks, 40 to 52 weeks), actual cumulative dose, ADI, RDI, and RDI categories (>80%, <=80%; >95%, <=95%).

Another summary table will be generated for dose increased, dose reduced, dose held, and the reasons.

A by patient listing will be generated for the detailed exposure information.

It will be summarized in Safety Population and by group.

3.8 Definition of Efficacy Endpoints

3.8.1 Primary Efficacy Endpoint: CRISS

The primary efficacy endpoint is Combined Response Index in Diffuse Cutaneous Systemic Sclerosis (CRISS).

CRISS is a 2-step process for use in a clinical trial.

Step 1: patients who develop new onset of renal crisis, new onset or worsening of lung fibrosis, new onset of pulmonary arterial hypertension, new onset of left ventricular failure during the trial are considered as not improved and assigned a probability of improving equal to 0.0.

Step 2: For the remaining patients, step 2 involves computing the predicted probability of

improving for each individual, using the equation shown below.

$$\frac{\exp\left[-5.54 - 0.81 * \Delta_{MRSS} + 0.21 * \Delta_{FVC\%} - 0.40 * \Delta_{Pt-glob} - 0.44 * \Delta_{MD-glob} - 3.41 * \Delta_{HAQ-DI}\right]}{1 + \exp\left[-5.54 - 0.81 * \Delta_{MRSS} + 0.21 * \Delta_{FVC\%} - 0.40 * \Delta_{Pt-glob} - 0.44 * \Delta_{MD-glob} - 3.41 * \Delta_{HAQ-DI}\right]}$$

where Δ_{MRSS} indicates the change in mRSS from baseline to follow up, $\Delta_{FVC\%}$ denotes the change in FVC% predicted from baseline to follow up, $\Delta_{Pt-glob}$ indicates the change in patient global assessment, $\Delta_{MD-glob}$ denotes the change in physician global assessment, and Δ_{HAQ-DI} is the change in HAQ-DI. All changes are absolute change (Time₂-Time_{baseline}).

As patient global assessment and physician global assessment are based on a VAS of 0 (Extremely Poor)-100 (Excellent) in CRF. When calculating the CRISS score, these 2 scores should be divided by 10 firstly to make it in a 0-10 scale. If any of the component scores are missing, CRISS score will be calculated based on the imputed component score using LOCF method.

The outcome is a continuous variable between 0.0 and 1.0 (0-100%). A higher score indicates greater probability of improvement. A CRISS score ≥ 20% is considered as the minimal detectable difference and will be described as CRISS20 in the SAP. A CRISS score >= 60% is considered as the minimally important difference and will be described as CRISS60 in the SAP. This will be the primary variable for efficacy.

Analyses of the primary efficacy endpoints will be conducted using the mITT population. The number and percentage of patients achieving CRISS60 response will be summarized by treatment group. Treatment comparisons between each belumosudil dose regimen and placebo in the proportion of patients achieving an CRISS60 response will be analyzed using a logistic regression analysis with treatment in the model.

The continuous CRISS score will be summarized as a continuous endpoint at all post baseline scheduled assessment visits. The continuous CRISS score will be analyzed using the MMRM model, and a t-test comparison. If the data is not normally distributed then the Wilcoxon-Mann-Whitney model will be used instead of a t-test. Missing data will be imputed using the Linearization method The linearization method will take the average of the last observation and the next non missing observation. If there is no next non missing observation in the current treatment group then just the last observation will be used.

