3.8.2.3 Physician Global Assessment

Physician global assessment is physician's assessment of patient's overall health during the last week based on a VAS of 0 (Extremely Poor)-100 (Excellent). A positive change from baseline demonstrates improvement.

Physician global assessment score, change from baseline, percent improvement will be summarized as a continuous endpoint at all scheduled assessment visits.

The change from baseline and percent improvement in physician global assessment score will be analyzed using the MMRM model. In addition, the change from baseline and percent improvement in physician global assessment score will be analyzed using the ANCOVA model. Missing data will not be imputed.

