3.8.2.4 Patient Global Assessment

Patient global assessment is patient's assessment of their overall health during the last week based on a VAS of 0 (Extremely Poor)-100 (Excellent). A positive change from baseline demonstrates improvement.

Patient global assessment score, change from baseline, percent improvement will be summarized as a continuous endpoint at all scheduled assessment visits.

The change from baseline and percent improvement in patient global assessment score will be analyzed using the MMRM model. In addition, the change from baseline and percent improvement in patient global assessment score will be analyzed using the ANCOVA model. Missing data will not be imputed.

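### The CRISS formula in SAP 3.8.1 gives both global assessments negative coefficients but scores them with 100 as best and never reverses them, so an improving global lowers the score

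*SAP*

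**What the plan says.** SAP 3.8.1 defines CRISS in two steps. Patients with certain new or worsening organ events are set to 0.0 (Step 1). For everyone else a logistic equation gives the predicted probability of improving (Step 2). Its coefficients are -0.81 for mRSS, +0.21 for FVC% predicted, -0.40 for the patient global, -0.44 for the physician global and -3.41 for HAQ-DI, with intercept -5.54.

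On direction and scaling, the SAP says:

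- Change scores: "All changes are absolute change", taken as follow-up minus baseline.
- Global scales in 3.8.1: "based on a VAS of 0 (Extremely Poor)-100 (Excellent) in CRF".
- Conversion before entry to the equation: "these 2 scores should be divided by 10 firstly to make it in a 0-10 scale".
- Output: "A higher score indicates greater probability of improvement".
- Physician global in 3.8.2.3: "based on a VAS of 0 (Extremely Poor)-100 (Excellent). A positive change from baseline demonstrates improvement". Section 3.8.2.4 gives the same anchors and direction for the patient global.

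No section of the SAP or the protocol reverses either global before it enters the equation.

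**The concern.** A component that rises with improvement needs a positive coefficient if the index is to rise with improvement. Both globals rise with improvement as the SAP describes them, yet both have negative coefficients. A programmer following 3.8.1 as written would score improvement in two of the five components as deterioration, and deterioration as improvement.

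CRISS is the primary endpoint. The error would reach the CRISS60 logistic regression, CRISS20, the continuous score (MMRM, and t-test or Wilcoxon) and the Week 52 CRISS objective in SAP 2.1.2. The study is exploratory and not sized by hypothesis testing (Protocol 9.7.2, SAP 3.1.3), so loss of power is secondary. Protocol 9.7.1 says its main purpose is to guide follow-up studies, and a primary index that does not measure improvement in two of its components cannot do that reliably.

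**Working it through.** **Inputs.** All coefficients, the definition of change, the anchors and the division by 10 come from SAP 3.8.1. The direction of improvement comes from 3.8.2.1 (mRSS), 3.8.2.3 and 3.8.2.4 (globals) and 3.8.2.5 (SHAQ-DI). The documents give no worked CRISS value, so there is no plan figure to reproduce. They also give no expected component changes, so the patient profiles and simulation inputs below are assumptions.

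**Step 1: sign of each component**

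| Component | Change that is improvement | Coefficient | Improvement moves CRISS |
|---|---|---|---|
| mRSS | negative | -0.81 | up |
| FVC% predicted | positive | +0.21 | up |
| HAQ-DI | negative | -3.41 | up |
| Patient global | positive (as the SAP states) | -0.40 | **down** |
| Physician global | positive (as the SAP states) | -0.44 | **down** |

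Only the globals conflict.

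**Step 2: size on the logit scale.** Let

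`x = -5.54 - 0.81*dMRSS + 0.21*dFVC% - 0.40*dPt - 0.44*dMD - 3.41*dHAQ`, with `CRISS = exp(x)/(1 + exp(x))`.

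If both globals improve by 20 VAS points, dPt = dMD = +2 after division by 10.

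- As written: -(0.40 x 2 + 0.44 x 2) = -1.68.
- Reversed: +1.68.
- Gap: 2 x 1.68 = 3.36 logits, or 3.36/0.81 = 4.1 mRSS points.

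A 10-point improvement on both gives a gap of 1.68 logits, or 1.68/0.81 = 2.1 mRSS points.

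**Step 3: individual scores**

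*Profile 1:* mRSS -6, FVC% 0, HAQ-DI -0.2. Without the globals, x = -5.54 + 4.86 + 0.682 = 0.002.

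*Profile 2:* mRSS -7, FVC% 0, HAQ-DI -0.25. Without the globals, x = -5.54 + 5.67 + 0.8525 = 0.9825.

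| Profile | Change in both globals (VAS points) | CRISS as written | CRISS reversed |
|---|---|---|---|
| 1 | +20 | 0.157 | 0.843 |
| 1 | 0 | 0.500 | 0.500 |
| 1 | -20 | 0.843 | 0.157 |
| 2 | 0 | 0.728 | 0.728 |
| 2 | +10 | 0.536 | 0.861 |
| 2 | +20 | 0.332 | 0.935 |

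A Profile 2 patient is a CRISS60 responder with unchanged globals and, as written, stops being one once both globals improve by 10 points.

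**Step 4: illustrative effect on the comparison.** Assumptions: 20 per arm; SD 5 for mRSS, 5 for FVC%, 20 VAS points for each global and 0.4 for HAQ-DI; correlation 0.3 on the improvement scale; no Step 1 events. Mean improvements are listed as mRSS; FVC%; globals; HAQ-DI.

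| Scenario | Active | Placebo | CRISS60 active/placebo, reversed -> as written | Wilcoxon power, reversed -> as written |
|---|---|---|---|---|
| A | 5; 0.5; 10; 0.15 | 2; -1; 0; 0 | 47/22% -> 32/16% | 55% -> 35% |
| B | 4; 0; 15; 0.1 | 3; -1; 0; 0 | 43/26% -> 22/21% | 26% -> 5% |
| C | 6; 0; 3; 0.1 | 2; -1; 0; 0 | 47/22% -> 42/16% | 54% -> 64% |
| D | 5; 0.5; 0; 0.15 | 2; -1; 0; 0 | 41/22% -> 39/16% | 38% -> 56% |
| E | 5; 0.5; 5; 0.15 | 2; -1; 0; 0 | 44/22% -> 36/16% | 47% -> 44% |
| No effect | 2; -1; 0; 0 | 2; -1; 0; 0 | 22/22% -> 16/16% | 5% -> 4% (rejection rate) |

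In scenarios A to E, CRISS60 status flips for 14-22% of active and 11-12% of placebo patients. Repeating the simulation changed the power figures by no more than about 2 percentage points.

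**The case against.** The strongest objection is that the anchors may be what is wrong. The forms in Protocol Appendices D and E are not visible in this copy. If the CRF actually runs from good to bad, the equation is valid as it stands, and the faults lie in the anchor and direction statements. That stands as a limit on the conclusion: harm to the primary endpoint depends on the anchors being as the SAP states. It does not rescue the text. The SAP gives these anchors three times and the direction of improvement twice, and if they are wrong, the two secondary analyses of the globals would report worsening as improvement.

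Second, CRISS is calculated outside the EDC system (Protocol Section 5), so a programming specification may already reverse the globals. That is possible, and no wrong result has been shown. A primary endpoint should still not depend on a step that the plan omits.

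Third, a wrong sign alters the continuous score whenever the weighted global change is not zero, but it alters CRISS20 or CRISS60 only when the score crosses the cut. That is correct: in the simulation most patients keep their CRISS60 status.

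Fourth, the power figures rest wholly on assumed inputs and move in both directions, and Wilcoxon is only the fallback when the data are not normal. This also stands. They show that the direction of bias cannot be predicted; the sign conflict does not depend on them.

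**Conclusion.** The concern holds. The stated anchors, the change definition, the negative coefficients and the absence of a reversal cannot all be right if a higher CRISS is to mean improvement. With the anchors as stated, the continuous Step 2 score is wrong for every patient whose weighted global change is not zero, by 1.68 logits for each 10 VAS points of change on both globals, and some patients are misclassified on CRISS20 and CRISS60. Patients set to 0.0 in Step 1 are unaffected.

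The direction of bias in the treatment comparison is unknown, because the documents give no expected effect on the globals. In the illustrative scenarios the contrast shrinks when the globals improve clearly on drug and can grow when they do not, while the rejection rate under no effect stays near nominal. The logit shifts follow from the SAP alone; the individual scores and simulated rates rest on assumed values. The sections must be reconciled before CRISS is derived.

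**What to change.** 1. Check the anchors on the CRF forms for both globals.
2. If 100 is the best state, replace the scaling sentence in SAP 3.8.1 with: Reverse and rescale both globals as (100 - VAS)/10, then take follow-up minus baseline of the reversed score. Using +0.40 and +0.44 with the CRF direction is equivalent.
3. If a higher CRF score is worse, keep the equation and correct the anchors and the direction of improvement in 3.8.1, 3.8.2.3 and 3.8.2.4.
4. In either case, add a programming check that improving any one component, with the others fixed, raises the Step 2 score. Recompute any CRISS value already derived with the wrong direction.

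The cost is a look at two forms, one SAP sentence or three anchor corrections, and one line of derivation code. No new data are needed.
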